H5. There will also be a reduced bias towards sad emotional expressions (i.e. greater threshold change in favour of happy) following acute alcohol consumption compared to placebo (happy-sad 2AFC task).

Study Design

This is a placebo-controlled experimental study, which comprises one within-subjects factor of drink (0.4 g/kg alcohol, placebo) and one between-subjects factor of trait

anger (high, low). For the 6AFC task (see Measures and Materials), there will be an additional within-subjects factor of emotion (happy, sad, angry, disgust, surprise and fear). The primary dependent measures will be hit rate and false alarms (6AFC task) and threshold response (2AFC tasks). We will also take subjective measures of state aggression, mood and intoxication. For these outcomes, there will be an additional within-subjects factor of time (pre-consumption, post-consumption).

Study Site

School of Experimental Psychology, [name], Bristol University, [name].

Participants and Recruitment

Male and female social alcohol drinkers (n = 88; 50% male) will be recruited from the staff and students at the University of Bristol, and the general population. Participants will attend two sessions of approximately 75 minutes each. Participants will be recruited by existing email lists, poster and flyer advertisements, and by word of mouth. They will be asked to contact the researcher for further details of the study if they are interested in taking part. Those who meet the initial study inclusion criteria will be asked to complete a short online screening questionnaire. Participants that are eligible will be sent the information sheet, and asked to contact the researcher again if they would like to sign up for the study or if they require further information. Participants will be required to not drink alcohol 24 hours prior to the study session. On completion of the study, participants from the general population will be reimbursed £20 or equivalent course credits (if eligible).

Inclusion criteria

- Good physical and psychiatric health (self-report)
- Drinks between 5 and 35 alcoholic units* per week if female or between 10 and 50 alcoholic units* per week if male
- Aged between 18 and 40 years
- Be high or low in trait aggression, defined by a score above 41 and below 32 on the Anger Expression Index subscale of the State-Trait Anger Expression Inventory-2 (STAXI-2), respectively.
- Speaks English as first language or equivalent level of fluency

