- Able to attend two sessions, at least one week apart

* One unit equals one 25 ml single measure of spirit (ABV 40%), or a third of a pint of beer (ABV 5-6%) or half a standard (175 ml) glass of red wine (ABV 12%).

Exclusion criteria

- Alcohol consumption less than 24 hours prior to the study sessions
- Weight less than 50 kg if female or 60 kg if male
- Strong familial history of alcoholism defined as one or more immediate relative (parent, sibling) or more than one other relative (e.g., cousin, grandparent) (self-report)
- History of psychiatric disorder (including drug addiction) (self-report)

- Uncorrected visual impairment
- Uncorrected auditory impairment

Sample size determination

A sample size calculation based on previous findings from a study using a between-subjects design (Craig et al., 2009) indicates an effect size of $d = 1.0$ for the difference between alcohol and placebo on sadness recognition ($M = 0.14$, $SD = 0.02$; $M = 0.12$, $SD = 0.02$, respectively). These data indicate that we require a total sample size of 46 participants to achieve 90% power at an alpha level of 5%. As we are including a between-subjects factor, we plan to recruit sufficient numbers in each group to achieve this level of power to observe a main effect of alcohol. However, as this is likely to be an inflated effect size, we used a more conservative effect size estimate of $d = 0.7$. Based on this estimate, 88 participants would be required in each drink condition in a between-subjects design to achieve 90% power at an alpha level of 5%. However, as our alcohol/placebo condition will be within-subjects, we consider this a conservative estimate for our study, as we are using a within-subject design that will be less subject to less individual variation. We will recruit 44 participants per trait group (total $n = 88$). This would achieve 90% to detect an effect size of $d_z = 0.5$ (alcohol vs. placebo) within each trait group. Interaction analyses will be exploratory.

Withdrawal of participants

Participants will be informed that they can withdraw from the study at any time. If participants withdraw from the study due to an adverse event or reaction, they will receive full reimbursement (£20 or equivalent course credits). For all other withdrawals (i.e., not related to an adverse event or reaction), participants will be reimbursed an amount commensurate with the time spent in the laboratory.

Randomisation

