Session order (i.e., alcohol vs. placebo) will be counterbalanced with equal numbers of participants in each order group. Participant numbers will be allocated session orders in advance of the study using random number generator software (www.randomizer.org).

Measures and Materials

Computerised Tasks: The images used in both tasks are composite (i.e., prototypical) images created from photographs of 12 young male adults photographed under controlled conditions. Each trial in both tasks begins with a centrally-displayed fixation cross. A 350×457 pixel face stimulus is then presented for 150 ms, followed by a noise mask for 250 ms in order to prevent after-image effects. Tasks are run using E-Prime 2.0 Pro software, on a standard computer with a QWERTY keyboard.

In the six-alternative forced choice task (6AFC), six 15-image morph sequences have been created, one for each emotion (happy, sad, angry, disgust, surprise and fear). These run along a linear continuum from a neutral (i.e., emotionally ambiguous) prototype to the full emotional intensity. On each trial, a single image from the 90

available is presented for 150ms (backward masked), and participants are required to identify the emotion represented in the face as quickly and as accurately as possible, by using the mouse to click on the most appropriate descriptor from an array of descriptors displayed on-screen (happy, sad, angry, disgust, surprise and fear). The descriptor array appears on-screen for 10,000 ms, or until the participant responds. Each image is presented twice, giving 180 trials in total.

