Computerised Tasks: Total hits and thresholds will be assessed for outliers using boxplots. Participant data will be removed if scores are 1.5 times greater than the interquartile range. Data will also be assessed for Normality using skewness and kurtosis statistics. Where Mauchly's Test of Sphericity is $p < .05$, Greenhouse-Geisser corrected statistics will be reported.

For 6AFC analysis, total hits will be analysed using a 2 drink (alcohol, placebo) \times 2 aggression (high, low) mixed model ANOVA to test emotion processing accuracy following an acute dose of alcohol. Interactions will be explored in post-hoc analyses using t-tests. To investigate processing accuracy of angry and sad faces following an acute dose of alcohol, emotion specific false alarms and hit rates will also be analysed using 2 drink (alcohol, placebo) \times 2 aggression (high, low) mixed ANOVAs; two for anger and two for sadness. The 2AFC data will be analysed using the same statistical model as the 6AFC total hit rate data to investigate whether there is an increased bias towards anger (happy-angry 2AFC) and a reduced bias towards sadness (happy-sad 2AFC) following an acute dose of alcohol. In addition, 6AFC hit rates will also be

analysed using an exploratory 2 drink (alcohol, placebo) × 2 aggression (high, low) × 6 emotion (happy, sad, angry, disgust, surprise, fear) mixed model ANOVA.

Questionnaire data will be analysed using 2 drink (alcohol, placebo) × 2 aggression (high, low) × 2 time (pre-consumption, post-consumption) mixed model ANOVAs. Interactions will be explored in post-hoc analyses using t-tests. Correlations between post-consumption state anger (S-Ang scores) and false alarms/hit rates (6AFC task) will be analysed using simple linear regression models.

Ethical Considerations and Informed Consent

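### The drink ANOVAs leave out session order, and order balance is assured only overall: an avoidable loss of efficiency, mainly in the within-trait-group contrasts

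*Protocol*

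**What the plan says.** The Study Design section describes a crossover in drink with a trait group factor: the study is one "which comprises one within-subjects factor of drink (0.4 g/kg alcohol, placebo) and one between-subjects factor of trait" anger. It names the main outcomes: "The primary dependent measures will be hit rate and false alarms (6AFC task) and threshold response (2AFC tasks").

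The Randomisation section states: "Session order (i.e., alcohol vs. placebo) will be counterbalanced with equal numbers of participants in each order group". It adds: "Participant numbers will be allocated session orders in advance of the study using random number generator software". It does not mention trait group.

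The Statistical Plan section begins the confirmatory task models with "For 6AFC analysis, total hits will be analysed using a 2 drink (alcohol, placebo") crossed with aggression (high, low). The anger and sadness hit rates and false alarms have the same two factors. For the other tasks, "The 2AFC data will be analysed using the same statistical model as the 6AFC total hit rate data". The exploratory six-emotion ANOVA adds emotion, and the questionnaire ANOVAs add time before and after the drink. None has a session or order term.

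The Sample size determination section sets the numbers: "We will recruit 44 participants per trait group (total $n = 88"). It then claims: "This would achieve 90% to detect an effect size of $d_z = 0.5$ (alcohol vs. placebo) within each trait group". It declares interaction analyses exploratory.

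**The concern.** The two sessions use the same images and the same three tasks, and the timeline in the Procedure section shows no practice run. Some average change from the first session to the second is therefore plausible, although the protocol gives no estimate of it.

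In a two-period crossover such a change raises the alcohol-minus-placebo difference in one order group and lowers it in the other. A model without order treats that systematic spread as random error. The stated 90% within each trait group has no reserve to absorb this, because 44 is the smallest number that reaches it.

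The second issue is the order split inside each trait group. Equal orders across all 88 do not guarantee 22:22 in the high and low groups. If the split is uneven, part of the session change stays in that group's drink contrast and, with opposite sign, in the other group's.

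The statistical analysis plan is not at hand. But the protocol itself lists the factors of each model, so this is not merely detail left for later.

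**Working it through.** **Inputs from the protocol.** 44 per trait group, 88 in total; dz = 0.5; alpha 5%; equal numbers in each order, so 44:44 overall.

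**Assumption.** π is the mean change from session 1 to session 2, in SDs of the paired difference within an order group. The protocol gives none, so a range is shown.

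**1. The protocol's own figure.** Two-sided paired t-test, noncentrality 0.5 × √44 = 3.317, df 43: power 0.900. With 43 participants it is 0.893. The stated 90% reproduces.

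**2. Error inflation.** Write D for a participant's alcohol-minus-placebo difference. Then D = δ + π + e if alcohol comes second and D = δ − π + e if it comes first, with Var(e) = 1. At 22:22 the mean of D is still δ, but the pooled variance is about 1 + π². The effective dz is therefore 0.5 / √(1 + π²). The noncentral-t calculation with this dz is slightly pessimistic, because the shift inflates the estimated variance but adds no noise to the mean. Simulation at 22:22 allows for this.

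| Assumed π | √(1 + π²) | Effective dz | Within-group power, order omitted: approximation | Simulation | Order included (df 42) |
|---|---|---|---|---|---|
| 0.3 | 1.04 | 0.479 | 0.87 | 0.88 | 0.90 |
| 0.5 | 1.12 | 0.447 | 0.83 | 0.85 | 0.90 |
| 0.8 | 1.28 | 0.390 | 0.72 | 0.76 | 0.90 |

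**3. Drink main effect, all 88.** With 44:44 orders and 44 per trait group, a split of 22 + k : 22 − k in one group forces 22 − k : 22 + k in the other. The biases +2kπ/44 and −2kπ/44 cancel, so the main effect has no bias. With order omitted its simulated type I error is 0.040, 0.028 and 0.012 at π = 0.3, 0.5 and 0.8, so the test is conservative. Its power at dz = 0.5, by the approximation, is 0.993, 0.986 and 0.95.

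**4. Chance imbalance within a trait group.** This step assumes one list, balanced 44:44 overall and not stratified by trait. The number with a given order in a trait group is then hypergeometric (88, 44, 44), with mean 22 and SD 2.36.

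- Exactly 22:22: probability 0.17.
- 25:19 or worse: probability 0.286.
- 27:17 or worse: probability 0.054.

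The bias in a group's drink contrast is (difference in order counts / 44) × π. The difference between the two groups' contrasts, which is drink × aggression, carries twice that.

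- At 25:19: 6/44 = 0.14π within group; 12/44 = 0.27π for drink × aggression.
- At 27:17: 10/44 = 0.23π and 20/44 = 0.45π.

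Given a 27:17 split, the type I error of drink × aggression with order omitted is 0.080, 0.128 and 0.206 at π = 0.3, 0.5 and 0.8. Averaged over all unstratified lists it is 0.051, 0.051 and 0.053, which is nominal.

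**5. With order in the model.** At 27:17 the simulated type I error returns to 0.045–0.053 for the main effect, the interaction and the within-group contrast.

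**The case against.** The case on the other side is substantial.

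- **H1 to H5 are safe from bias as planned.** All five compare alcohol with placebo and none concerns trait. A reader might infer that a practice effect could pass for a drink effect. With complete data and 44:44 orders it cannot: the bias is zero and the test is conservative. Unequal withdrawals or outlier removals could unbalance order, but the protocol gives no rate for either.
- **Power for those hypotheses is hardly touched.** A reader might take the within-group losses as losses for every hypothesis. The main effect uses all 88, and its power stays above 90% even at a shift of 1.0 SD.
- **The protocol does not say that order is unbalanced within trait group.** It is silent. Only the weaker statement, that balance there is not assured, is supported, and the 29% applies only if the list is not stratified.
- **The interaction is exploratory.** Its type I error averaged over lists is nominal, so a claim of a generally raised false-positive rate would be wrong.
- **The shift is assumed.** At 0.3 SD the loss is two or three percentage points. A shift is also less obvious for 2AFC thresholds, which measure bias rather than accuracy.

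All of this stands. What remains is that the protocol makes its 90% claim within each trait group, where the loss is largest and chance imbalance matters. The analyst will also have one realised list, not the average over lists.

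**Conclusion.** The point holds as one of efficiency, not of validity for the stated hypotheses. The protocol fixes two-session crossover models without session or order, so any session shift erodes the power stated within each trait group. It also leaves a bias in the within-group and drink × aggression contrasts that depends on the order split actually drawn. The size of both effects rests on the assumed shift, and the imbalance probabilities rest on a list not stratified by trait. The omission and the direction of its effect rest on no such assumption. It should be treated as a free improvement to make, not as a defect that undermines H1 to H5.

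**What to change.** Add order group as a between-subject factor to every drink ANOVA, including those for the questionnaires. The drink × order term must be in the model, since that term is the session effect; an order main effect alone would not remove it. Adjust the within-trait-group contrasts for order in the same way. This restores within-group power at dz = 0.5 to about 0.90 and removes the bias from an uneven split.

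State that the order list is generated separately for high and low trait participants, 22:22 in each. Stratifying by sex as well is optional and not part of this fix.

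The cost is one error degree of freedom for drink × order (43 to 42 within a trait group, 86 to 85 overall) and two lists from the same random number generator in place of one. No extra participants are needed. If recruitment has already begun, the model change alone still recovers the power and removes the bias.

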Prior to testing, participants will complete the STAXI-2 online. Only individuals that meet the high/low trait anger inclusion criteria will be invited to participate. On arrival at the first session, participants will be given the opportunity to read the information sheet again and ask questions, before providing written informed consent. The researcher will conduct a short screening procedure to verify eligibility, which includes taking measures of weight and breath alcohol concentration (BrAC) (only participants with a BrAC of zero will be enrolled). Study documentation from failed screenings will be destroyed using the School's confidential waste facility. If eligible, participants will complete questionnaire measures (AUDIT, PANAS, BAES, S-Ang).

Participants will attend two sessions (order counterbalanced): at one session they will consume an alcoholic drink and at the other they will consume a matched placebo drink (see Drug Administration section for more details). Testing sessions will be held at least one week apart. Participants will be given 10 minutes to consume all of their drink and a further 10 minutes to sit quietly to allow for absorption. After drink consumption, participants will complete the 6AFC and 2AFC tasks. They will then complete questionnaire measures (PANAS, BAES, S-Ang), and a BrAC reading. Before leaving the session, participants will be required to read and sign a safety card, be offered the opportunity to stay behind until they feel any effects of alcohol have worn off and be offered a taxi home. At the end of session two, participants will be debriefed and reimbursed.

Table 1: Testing procedure timeline

Time (min)	Activity/Task
0	Informed consent and screening (session one only)
10	Questionnaire measures (AUDIT, PANAS, BAES, S-Ang)
20	Drink administration
30	Alcohol absorption period
40	Computerised tasks
65	Questionnaire measures (PANAS, BAES, S-Ang), BrAC reading
75	Debrief and reimbursement (session two only).

Drug Administration

The alcoholic drink will be 0.4 g/kg alcohol (vodka) with one part vodka and three parts tonic water. The placebo drink will comprise the same volume of tonic. Drinks will be flavoured with lime cordial and chilled prior to serving. The rim of the glass will be sprayed with a vodka mist. Drinks will be served double blind and will be made at the start of each session by a research collaborator.

Statistical Plan

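### Questionnaire outcomes: entering the pre-drink score as a level of time, instead of adjusting for it, generally gives a less precise drink effect

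*Protocol*

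**What the plan says.** All references are to the protocol.

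- **Study Design** names the primary measures: "The primary dependent measures will be hit rate and false alarms (6AFC task) and threshold response (2AFC tasks". It then adds: "We will also take subjective measures of state aggression, mood and intoxication". For the latter only, "For these outcomes, there will be an additional within-subjects factor of time (pre-consumption, post-consumption".
- **Statistical Plan** turns this into a model for the questionnaire data: drink (2) × aggression (2) × "2 time (pre-consumption, post-consumption) mixed model ANOVAs". Interactions are followed up with post-hoc t-tests. The plan does not say which term answers the drink question, and it nowhere uses the pre-drink score as a covariate.
- **Procedure and Table 1** place "questionnaire measures (AUDIT, PANAS, BAES, S-Ang") at minute 10, the drink at minute 20, and "Questionnaire measures (PANAS, BAES, S-Ang), BrAC reading" at minute 65. Table 1 restricts only consent and screening to session one, and debrief and reimbursement to session two. I therefore read the pre-drink PANAS, BAES and S-Ang as taken at both sessions, which the planned model also requires.
- **Randomisation**: "Session order (i.e., alcohol vs. placebo) will be counterbalanced with equal numbers of participants in each order group". Orders are allocated in advance by random number generator.

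**The concern.** A drink cannot change a score recorded before it is served. Making that score a level of the outcome has two consequences.

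First, the term labelled drink averages an unaffected pre-drink difference with the post-drink difference. A reader who takes that line of the ANOVA table sees a diluted effect.

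Second, the term that isolates the drink effect, drink × time, compares change scores. A change score subtracts the whole pre-drink score, which fixes its slope at 1 whatever the data show. Estimating the slope uses the same data and, apart from one degree of freedom, cannot be less precise.

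At stake is the width of the intervals for state anger, mood and subjective intoxication, and clarity about which number is the drink effect.

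**Working it through.** **The plan's own figure.** The protocol gives no power for the questionnaires. Its only related figure is 90% power for d_z = 0.5 with 44 participants per trait group (Sample size determination). A paired t-test, two-sided 5%, noncentral t with 43 degrees of freedom, gives 90.0%, so that figure reproduces. It is not a statement about these outcomes.

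**Notation.** For each participant let D_pre and D_post be the alcohol-minus-placebo differences in the pre-drink and post-drink score. Let v be the variance of D_post, k = SD(D_pre)/SD(D_post), and r = corr(D_pre, D_post). The documents give neither k nor r. Let δ be the mean of D_post. The mean of D_pre is 0, because order is randomly allocated and balanced.

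**Step 1: drink main effect.** It estimates the mean of (D_pre + D_post)/2, which is (0 + δ)/2 = δ/2.

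**Step 2: drink × time.** It tests D_post − D_pre, which has mean δ (unbiased) and variance v(1 + k² − 2kr).

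**Step 3: baseline-adjusted effect.** Regressing D_post on D_pre also estimates δ, with residual variance v(1 − r²).

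**Step 4: ratio, planned over adjusted.**

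(k² + 1 − 2kr)/(1 − r²) = 1 + (k − r)²/(1 − r²)

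The second form shows that the ratio is never below 1, and equals 1 only when k = r. With k = 1 it reduces to 2/(1 + r).

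**Step 5: numbers.** Power is that of the planned drink × time test at n = 88, where the adjusted test has 90% (noncentral t, 86 degrees of freedom, noncentrality divided by the square root of the ratio).

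| r | k = 1: ratio, power | k = 0.7: ratio, power | k = 0.5: ratio, power |
|---|---|---|---|
| 0 | 2.00, 63% | 1.49, 76% | 1.25, 83% |
| 0.3 | 1.54, 74% | 1.18, 85% | 1.04, 89% |
| 0.5 | 1.33, 80% | 1.05, 88.5% | 1.00, 90% |
| 0.8 | 1.11, 87% | 1.03, 89% | 1.25, 83% |

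Worked entry, k = 0.5 and r = 0.3: (0.25 + 1 − 0.30)/(1 − 0.09) = 0.95/0.91 = 1.04.

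The ratio can also exceed 2. At k = 1 and r = −0.2 it is 2.4/0.96 = 2.5.

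**Step 6: which r is relevant.** It is the correlation of between-session differences, from which stable differences between people have already cancelled. If person, session and residual variances were 0.5, 0.1 and 0.4 (an illustration, not protocol figures), the raw pre-post correlation would be (0.5 + 0.1)/1.0 = 0.60, but r = 0.1/(0.1 + 0.4) = 0.20.

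**Step 7: simulation** (n = 88, trait group in the model, k = 1, 3000 runs each). The variance of the adjusted estimate over the planned one was 0.59, 0.76 and 0.86 at r = 0.20, 0.50 and 0.67. Theory, (1 + r)/2, gives 0.60, 0.75 and 0.83. Both estimators were unbiased.

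**The case against.** The strongest reply is that nothing confirmatory is touched and that the planned test is sound. Both parts stand. A reader might infer that the questionnaire analysis is biased or has the wrong type I error, or that the trial's main conclusions are at risk. The documents support neither inference. Order is randomised and balanced, so drink × time is unbiased and valid. H1 to H5 rest on the 6AFC and 2AFC tasks, which have no pre-drink measurement.

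A second reply is that a doubling of variance is one corner of an unknown range. This also stands. A reader might take 2 as a general upper bound, but it is a bound only for k = 1 and r ≥ 0. The loss vanishes when k = r, and can exceed a factor of 2 when r is negative or k is above 1. A smaller pre-drink spread (k below 1) is plausible for an intoxication scale completed before drinking, although the protocol gives no distributions.

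A third reply is that the planned post-hoc t-tests can compare alcohol with placebo at post-consumption, undiluted. They can. Relative to the adjusted estimate, the variance of that contrast is 1/(1 − r²): 1.00, 1.10, 1.33 and 2.78 at r = 0, 0.3, 0.5 and 0.8. At low r it therefore recovers nearly everything. But it is only a follow-up to an interaction, and it ignores the baseline.

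Finally, the protocol does not name the drink main effect as its test. The dilution is therefore a risk of misreading, not a stated error.

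**Conclusion.** The point holds as one of efficiency and clarity, confined to the supportive questionnaire outcomes. The plan fixes a model whose drink line is half the post-drink effect. Its informative term is, apart from one degree of freedom, never more precise than baseline adjustment and usually less so.

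The size cannot be fixed from the protocol. Over the k and r tabulated, the variance ratio runs from 1.00 to 2.00, and planned power from 90% down to 63% where the adjusted test has 90%. The result assumes pre-drink scores at both sessions, the randomised balanced order the protocol describes, and a linear relation between the pre-drink and post-drink differences. The change is worth making because it is nearly free, not because the planned test is wrong.

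**What to change.** In the Statistical Plan, make the main questionnaire analysis of the drink effect (PANAS, BAES, S-Ang) a model of the post-consumption score with drink, trait group, drink × trait group and the pre-consumption score. The pre-consumption score should enter as the session's own baseline plus the person's mean baseline. Equivalently, regress the alcohol-minus-placebo post-consumption difference on the pre-consumption difference and trait group, with trait group coded −1/+1 so that the intercept is the drink effect averaged over the groups. In a simulated data set of 88 the two forms gave the same drink and drink × trait group estimates. Report the adjusted drink effect with its interval.

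The 2 × 2 × 2 ANOVA may stay as a descriptive supplement if the time and aggression × time terms are of interest.

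Cost: plan wording and no new data. The model carries one extra covariate term in the difference form or two in the mixed-model form, and the time terms leave the main model. A missing pre-drink score needs a handling rule, as it does under the planned ANOVA.

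### The one-predictor regressions of 6AFC scores on state anger do not fit a two-session, two-group design, so a significant slope could not be attributed to state anger

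*Protocol*

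**What the plan says.** All references are to the protocol.

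- **Statistical Plan**, last sentence: "Correlations between post-consumption state anger (S-Ang scores) and false alarms/hit rates (6AFC task) will be analysed using simple linear regression models". No drink, trait or participant term is named, and nothing says whether the fits are split by session or by group. The sentences just before it analyse the questionnaire data with drink, aggression and time in the model.
- **Study Design**: the study has "one within-subjects factor of drink (0.4 g/kg alcohol, placebo) and one between-subjects factor of trait" anger (high, low).
- **Procedure**: "at one session they will consume an alcoholic drink and at the other they will consume a matched placebo drink". The 6AFC task follows the drink at each session, and after the tasks "They will then complete questionnaire measures (PANAS, BAES, S-Ang), and a BrAC reading". Each participant therefore supplies two post-consumption S-Ang scores and two sets of 6AFC scores.
- **Inclusion criteria**: the trait groups are "defined by a score above 41 and below 32 on the Anger Expression Index subscale" of the STAXI-2, so the middle of the scale is left out. Under Measures and Materials, S-Ang is a subscale of the same inventory.
- **Sample size determination**: 44 participants per trait group, 88 in all.

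**The concern.** A simple linear regression has one predictor, so the stated model has no place for the three features that define this design: the person, the drink and the trait group.

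The protocol itself expects two of these to move the outcome. H2 predicts more anger hits and false alarms after alcohol, and the Background says that sober people high in self-reported aggression misidentify anger more often. If drink or trait group also moves S-Ang, the slope picks up that common movement.

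This is the only planned analysis that links felt anger to the recognition scores, and the Background presents altered emotion processing as a possible mechanism for alcohol-related aggression. A significant slope would readily be read as support for that mechanism, when it might show only that one trait group, or one session, scores higher on both measures.

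**Working it through.** **Figures in the plan.** The protocol gives no figure for the regression. Its nearby power statement (44 per group, dz = 0.5, 90%) reproduces: a paired t-test at two-sided 5% has power 0.900, and the required n is 43.995, so 44. The sample size used below is therefore sound.

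**Inputs from the protocol.** 88 people (44 + 44), two sessions each, so 2 × 88 = 176 rows if pooled; alpha 5%, taken as two-sided.

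**Assumptions.** The protocol gives neither the within-person correlation r between sessions nor any drink or trait shift on S-Ang or the 6AFC scores. Here r is taken as equal for both variables, and shifts are in SD units, equal and in the same direction on both.

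**Reading 1: both sessions pooled.** With two rows per person, no shifts and no true association, the variance of the slope is inflated by 1 + r·r. The actual rejection rate is 2·[1 − Φ(1.96/√(1 + r²))].

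- r = 0.5: 1 + 0.25 = 1.25; 1.96/1.118 = 1.753; rate 8.0%.
- r = 0.7: 1 + 0.49 = 1.49; 1.96/1.221 = 1.606; rate 10.8%.

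A simulation of 20,000 data sets per scenario gives 7.7% and 11.0%. At r = 0.3 the formula gives 6.1% and the simulation 6.2%. A drink shift on both variables adds to this: with r = 0, the pooled rejection rate is 6.0% at 0.3 SD and 12.0% at 0.5 SD.

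**Reading 2: one model per session.** Each person appears once and drink is constant. With no trait shift, the simulated rate in the alcohol session is about 5%, so the standard error is valid. The trait contrast remains. With two equal groups shifted by d on both variables, and no link inside either group, the groups add d²/4 to the covariance and to each variance:

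marginal correlation ρ = (d²/4) / (1 + d²/4)

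- d = 0.3: 0.0225/1.0225 = 0.02.
- d = 0.5: 0.0625/1.0625 = 0.06.
- d = 0.8: 0.16/1.16 = 0.14.

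The simulated chance of a significant slope in 88 people is 5.6%, 8.6% and 25%. This is power to detect a correlation that does exist in the sample but comes wholly from the groups.

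**Analyses that respect the design, same scenarios.** Rejection rates stay near 5%: change-on-change regression 4.8 to 5.2%, one session adjusted for trait group 4.9 to 5.3%, person means adjusted for trait group 4.7 to 5.2%. The change regression was simulated without a trait covariate, and the mixed model proposed below was not itself simulated.

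**The case against.** The strongest reply has four parts.

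1. **Pooling is not stated.** The plural in the sentence allows one model per session, and which sessions enter could be settled in an SAP that is not shown. This stands: the 8% and 11% apply only if the rows are pooled. It does not dispose of the point, because the type of model is fixed in the protocol and the per-session reading leaves the trait contrast in the slope. Only fits split by both drink and trait group, or adjusted fits, would remove it, and the text provides for neither.
2. **A marginal correlation is a legitimate quantity.** The plan speaks of correlations and claims no trait-independent effect. State anger may also lie on the path from trait anger to perception, so adjustment answers a different question. This stands as well. The unadjusted slope is valid as description; what it cannot do is separate state anger from trait group.
3. **The shifts may be small.** The Background calls the group's recent anger-bias effects after alcohol small, and H2 and H3 predict opposite directions for anger and sadness, so one common shift cannot describe every 6AFC outcome. At 0.3 SD the per-session rejection rate barely leaves 5%.
4. **Nothing primary depends on it.** H1 to H5 are tested by ANOVAs that include drink and aggression.

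A reader might infer something stronger: that the plan will report associations that do not exist, with error rates of a quarter or a third. The simulations do give 25% (one session, trait shift 0.8 SD) and 34% (pooled, r = 0.5, both shifts 0.5 SD). The documents do not support that reading. The shifts are assumed, the 34% also needs pooling, and the 25%, like the shift component of the 34%, is power to detect a real marginal correlation. Only the clustering part is true inflation of the false-positive rate.

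**Conclusion.** The point holds as a mismatch between a stated one-predictor model and a crossover in two selected groups.

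- **If pooled**, the test is anti-conservative: about 8% at r = 0.5 and 11% at r = 0.7 instead of 5%, with any common drink shift also entering the slope.
- **If fitted per session**, the test is valid for the marginal slope, but that slope mixes the trait contrast with any link between state anger and perception. The contrast alone gives a correlation of about 0.06 to 0.14 for assumed trait shifts of 0.5 to 0.8 SD, and about 0.02 at 0.3 SD.

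On either reading a significant slope could not be attributed to state anger. The sizes rest on assumed correlations and on equal, same-direction shifts in both variables. Confounding arises only if both variables move with drink or trait group. Because the analysis is secondary and the ANOVAs are untouched, the point is minor to moderate.

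**What to change.** Replace the simple regressions with one of these:

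- a linear mixed model for each 6AFC score, with a participant random intercept, drink and trait group as fixed effects, and S-Ang split into the person mean and the within-person deviation; or
- a regression of the alcohol-minus-placebo change in the 6AFC score on the alcohol-minus-placebo change in S-Ang, with trait group as covariate.

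Unadjusted correlations may still be reported for each session, labelled descriptive.

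The cost is a rewritten sentence and one or two degrees of freedom, on data already planned for collection. The target also changes: the slope becomes a within-person or trait-adjusted association instead of a marginal correlation, and the plan should say so.
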